Use of Convalescent Plasma Collected From Donors Recovered From COVID-19 Virus
Disease for Transfusion, as an Empirical and Preemptive Treatment during Viral
Pandemic Outbreak

Principal Investigator: [name]

Protocol version: 12/7/2020

Protocol Summary

Study Title: Use of Convalescent Plasma Transfusion, Collected From Donors Recovered From COVID-19 Virus Disease, as an Empirical and Preemptive Treatment during Pandemic Outbreak

Phase II

Expected Numbers of Patients:

Group 3: High risk patients n=159
Group 4: Health Care Providers n=152

Study Objectives:

- 1. To transfuse COVID-19 infected patients with convalescent plasma and to observe whether this will result in a significant improvement in clinical outcome in comparison to historical experience. Patients eligible include the following study groups:
- **Group 3:** As preemptive therapy for High Risk Patients who present with mild or non-severe COVID-19 infection.
- **Group 4:** As preemptive therapy for health care providers who have developed asymptomatic, mild or non-severe COVID-19 infection.
- **a. Primary objective** is whether infusion of convalescent plasma will reduce the probability of progressing to severe or critical disease significantly lower than the reported case rate (for Group 3 and 4, respectively).
- **b. Secondary objectives** are to determine if infusion of convalescent plasma will impact the patient's clinical course including days in hospital, days requiring ICU care, days on mechanical respirator/BIPAP, days on non-mechanical oxygen support, days with pneumonia, fever, and viral clearance.

Overview of Study Design

As of late 2019, the world population has been threatened by a life-threatening novel severe acute respiratory syndrome coronavirus 2 (SARS-CoV-2) that is abbreviated COVID-19. This virus is a new human pathogen with no known treatment available. Currently, there are no vaccines, monoclonal antibodies (mAb) or drugs available for COVID-19. While it is hoped that new drugs and vaccines will be developed and proven efficacious, these efforts will take many months to develop and test in clinical trials. Antimicrobial and immune modulating medications that are approved for other indications are being tested in clinical trials with the hope of abrogating the disease's progression to severe cardiopulmonary injury, but to date have not been shown to have definitive benefit. While there is no proven treatment available for COVID-19 virus disease, plasma collected from patients in the convalescent phase of infection has been used as an empirical treatment during viral pandemics for over one-hundred years with well documented benefit in reducing morbidity and mortality. 1,2 Most Individuals who recover from the viral infection develop humoral immunity with neutralizing antibodies that may persist for years. Collection of convalescent plasma and transfusion into an infected patient transfers immediate passive immunity, which was the only means to treat infections prior to the development of modern vaccine therapy. Not all patients benefit from convalescent plasma. Experience would indicate that the earlier in the course of illness convalescent plasma or immunoglobulin therapy was administered, the more likely benefit will be observed

with the highest benefit when used as prophylactic therapy.

In the past two decades there have been two epidemics with coronavirus that resulted in high mortality, SARS-1 in 2003 and Middle East respiratory syndrome (MERS) in 2012. The latter infections became an epidemic in the Middle East and triggered a secondary outbreak in South Korea. Due to the high mortality and lack of an effective therapy, convalescent plasma was utilized. The largest report involved 80 patients with severe SARS disease in Hong Kong. For patient who received convalescent plasma transfusion prior to day 14 of the infection have an improved prognosis and an earlier hospital discharge prior to day 22 (58.3% vs 15.6%, P<.001). The mortality rates in the two groups were 6.3% and 21.9%, respectively. This observation is consistent with the prior historical observations that earlier administration in the course of the infection is more likely to be effective.

China has offered convalescent plasma therapy for 245 COVID-19 patients, and 91 cases have shown improvement in clinical indicators and symptoms, per press report.³ Treatment of five critically ill patients in China with COVID-19 and acute respiratory distress syndrome (ARDS) with convalescent plasma was followed by resolution of ARDS in 4 patients within 9 days following transfusion.⁴ Of the 5 patients 3 had been discharged and 2 were in stable condition at 37 days post-transfusion. In a third report, 10 patients with severe COVID-19 infection received one dose of convalescent plasma derived from recently recovered donors.⁵ The primary endpoint was safety of plasma infusion and secondary endpoint was efficacy. Clinical symptoms improved along with improved oxygenation within 3 days of transfusion. The viral load was undetectable after transfusion in the seven of seven patients who had detection pretreatment at a median of 3 days (2-6 days). Cytokine surrogate marker, C-reactive protein, fell from a median before transfusion of 55.98 mg/L (nl range 0 – 6) to 18.13 following the treatment. No serious adverse reactions or safety events were recorded.

Group sequential design is employed for each hypothesis that analysis will be performed after enrolling and observing outcomes of one-third of maximum sample size. Our design includes two interim analyses and a final analysis for each hypothesis. The Pocock method is used to determine sample size and each study is sized to maintain the power of 80% and overall type I error 5%. To calculate the sample size, the large-sample Z test for a proportion is utilized for each analysis. The maximum number of enrollment for the four groups are: Group 1: 81, Group 2: 423, Group 3: 228 and Group 4: 219. Due to the likelihood that we may terminate a study for efficacy after an interim analysis, the expected numbers of enrollment for the four groups are 56, 296, 152 and 152, respectively.

[figure not shown]
Study Population: Eligible patients will be 18 years or older and must have a positive test result for COVID-19 infection to and meet the inclusion criteria described in Section 4.1

Duration of Study: 24 months

Participant Duration: 30 days or in the case of hospitalization, upon discharge; whichever

is longer.

Schema: Convalescent Plasma Treatment for COVID-19 Infection

Definitions:

COVID-19 severity categories:

- Mild No pneumonia but with typical symptoms such as fever, dry cough, fatigue, nausea, emesis or diarrhea.
- Non-severe Radiographic changes compatible with viral PNA, but no signs of respiratory compromise or hypoxemia.
- •Severe Respiratory compromise with one of the following: Tachypnea with RR ≥30, O₂ Sat ≤93% at rest, PaO₂/FiO₂ index ≤ 300 mmHg
- Critical One of the following: requiring mechanical ventilation, requiring pressor support, multiorgan failure.

Patient Risk Category:

High risk:

- •Immunocompromised (e.g. neutropenia, h/o hematopoietic stem cell transplant (<3 months post-autologous transplant, <6 months post-allogeneic transplant), on systemic immunosuppression, h/o solid organ transplant, Cancer patient receiving active chemotherapy, insulin dependent diabetes mellitus, poorly controlled HIV, moderate or severe asthma history, serious heart condition, ESRD on hemodialysis, morbid obesity, moderately severe or greater COPD.
- •Age ≥ 65 years

Contents

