3.0 Study Design

3.1 Overview of Study

COVID-19 infected patients will be screened per selection criteria shown in the Objectives and Study Population Sections. All patients must have confirmed COVID-19 disease and meet the inclusion and exclusion criteria established. Eligible patients for study after completing consenting process will be stratified into 4 treatment groups.

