3.2 Number of Patients

The number of patients expected per each of the 2 groups:

Group 3: High Risk: n=159
Group 4: Health Care Providers: n=152

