4.0 Study Population

4.1 Inclusion Criteria for the selection of COVID-19 Infected Patients for Convalescent Plasma Transfusion

Each patient must meet all of the following inclusion criteria to be enrolled in the study:

- 1. Age ≥ 18 years
- 2. Documented COVID-19 infection with nasal pharyngeal sampling test by real time reverse transcription polymerase chain reaction (rRT-PCR), or nucleic acid amplification technology (NAAT) molecular testing. A partial list of available tests can be accessed at https://www.fda.gov/medical-devices/emergency-use-authorizations
- 3. Have COVID-19 Disease criteria that meets one of the 2 following groups:

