6.0 Statistical and Quantitative Analysis

6.1 Determination of Sample Size and Statistical Analysis

Group sequential design is employed for each hypothesis that analysis will be performed after enrolling and observing outcomes of one-third of maximum sample size. Our design includes two interim analyses and a final analysis for each hypothesis. The Pocock method is used to determine sample size and each study is sized to maintain the power of 80% and overall type I error 5%. To calculate the sample size, the large-sample Z test for a proportion is utilized for each analysis.

	Enrollment at stage 1	Enrollment at stage 2	Enrollment at stage 3	Maximum enrollment	Expected enrollment for projected proportion
Study group 3	76	76	76	228	159
Study group 4	73	73	73	219	152

Group 3

For high-risk COVID-19 infected patients that present with early mild or non-severe disease the estimated percent who will develop severe disease is 27% for those over age 65. There is insufficient data on patients who have coexisting severe immune compromised status; however, for patients that presented with diabetes or heart disease/hypertension risk was 16% - 30%, respectively. Assuming a reported risk of progression of 25%, it is postulated that the infusion of convalescent plasma will reduce the probability for progression to severe disease by a factor of 0.35 to 16.3% or lower. We will carry out 3-stage of enrollment and 76 patients are enrolled in each stage. The interim analysis will be performed after enrolling and observing outcomes of 76 patients. Our design leads to the maximum size of 219 patients after completing 3-stage of enrollment and the expected size is 159 patients.

Group 4

Among healthcare workers 14.8% of cases were classified as evolving to severe or critical per the Chinese epidemiological review. ^{24,25} It is postulated that the infusion of convalescent plasma will reduce the probability for progression from asymptomatic, mild or nonsevere disease to that of severe disease will be reduced by a factor of .5 to 7.5% or lower. We will carry out 3-stage of enrollment and 73 patients are enrolled in each stage. The interim analysis will be performed after enrolling and observing outcomes of 73 patients. Our design leads to the maximum size of 219 patients after completing 3-stage of enrollment and the expected size is 152 patients.

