6.3 Statistical Analysis

We will perform intention-to-treat analysis to analyze outcomes of all enrolled patients. The primary analysis is to evaluate the CRF or disease progression rate against the null proportion. We plan to perform two interim analyses and one final analysis. The first interim analysis will be performed after enrolling and observing outcomes of one-third of maximum sample size. At an interim analysis, CRF or disease progression rate will be reported, together with a score confidence interval for the rate. The critical value used to evaluate the confidence interval is 2.289 based on the Pocock method. We will compare the upper limit of the confidence interval with the assumed null proportion. We will conclude efficacy of the treatment if the upper limit is less than the null proportion and terminate enrollment for the relevant study group. If the upper limit is greater than the null proportion, we will proceed to the second stage of enrollment and then perform the second interim analysis on the cumulative data. The same evaluation will be replicated in the second interim analysis, as well as in the final analysis should we proceed to this step.

After completing the trial, we will conduct secondary analysis to compare outcomes of this trial with published historical experience. We will use the score test for comparing two proportions in each evaluation. We will report both p value and 95% score confidence interval for difference between two proportions.

It is acknowledged that COVID-19 viral pandemic outbreak remains dynamic. Epidemiological update reports from the CDC may result in reassessment for case fatality rates as well as case rates for disease progression used in our study design that may require adjustments in sample size determinations at the interim analysis as independently allowed by the biostatistician.

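### Trial size is stated inconsistently: the Summary headline and Section 3.2 give only conditional averages (159 and 152), leftover four-group figures remain, and the planned two-group maximum of 228 + 219 = 447 is not stated where size is given

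*Combined protocol and SAP*

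**What the plan says.** The size of the trial is given in four places.

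- **Protocol Summary, headline numbers.** "Group 3: High risk patients n=159", with 152 for Group 4 on the next line. The list is labelled as expected numbers. It gives no maximum and no assumed progression rate.
- **Protocol Summary, design paragraph.** "The maximum number of enrollment for the four groups are: Group 1: 81, Group 2: 423, Group 3: 228 and Group 4: 219". Expected sizes follow for the same four groups: 56, 296, 152 and 152. The paragraph explains that the expected sizes are lower because a group may stop early for efficacy.
- **Section 3.2.** "The number of patients expected per each of the 2 groups", followed by 159 and 152 only.
- **Section 6.1.** A table for Groups 3 and 4 gives stages of 76 and 73, maxima of 228 and 219, and expected sizes of 159 and 152. Its column heading ties the expected sizes to the projected proportion. The Group 3 text below the table gives a maximum of 219.

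On the number of groups, Section 3.1 says eligible patients "will be stratified into 4 treatment groups", while the Section 4.1 inclusion criterion reads "Have COVID-19 Disease criteria that meets one of the 2 following groups". Groups 1 and 2 have no objective, endpoint, eligibility criteria or null rate in this version.

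On the design, Section 6.1 says "Our design includes two interim analyses and a final analysis for each hypothesis" and "each study is sized to maintain the power of 80% and overall type I error 5" per cent. Section 6.3 adds: "The critical value used to evaluate the confidence interval is 2.289 based on the Pocock method". Enrolment in a group stops at a look only if the upper confidence limit lies below the null rate; otherwise it goes on to the next stage.

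**The concern.** A reader who goes to the Summary headline or to the section on number of patients finds 159 and 152, and may take their sum, 311, as the planned size. Those figures are averages over early efficacy stops, worked out at one assumed benefit. If the benefit is smaller the average is larger, and if there is none nearly every trial runs to its maximum. A reader who goes instead to the Summary's design paragraph finds maxima for four groups that sum to 951, of which two groups no longer exist.

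What is at stake is the third stage. If 159 and 152 were read as targets, the last planned analysis would not be reached as designed and the stated power would not hold. Two further slips make the correct figure harder to recover: Group 3 has two expected sizes (152 and 159) and two maxima (219 and 228).

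**Working it through.** **Inputs.** From Section 6.1: null rates 25% (Group 3) and 14.8% (Group 4); projected rates 16.3% (0.65 × 25% = 16.25%) and 7.5%; three equal stages of 76 or 73; 80% power; overall type I error 5%. From Section 6.3: critical value 2.289 and efficacy-only stopping. Sidedness is not stated; 2.289 matches the three-look Pocock constant for two-sided 5% (one-sided 2.5%).

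**1. Reproducing the plan's figures.** With three equal looks at 2.289, 80% power needs a drift of 3.025. Using the null variance,

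N(max) = 3.025² × p0(1 − p0) / (p0 − p1)²

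- Group 3: 9.151 × 0.1875 / 0.087² = 226.7, rounded up to a multiple of 3: **228**.
- Group 4: 9.151 × 0.1261 / 0.073² = 216.5, rounded up likewise: **219**.

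The expected size is N(max) × (1 + P(pass look 1) + P(pass look 2)) / 3. At the projected rates the normal approximation gives (1 + 0.706 + 0.399) / 3 = 0.7018.

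- Group 3: 0.7018 × 226.7 = **159.1**.
- Group 4: 0.7018 × 216.5 = **152** (rounded).

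So 228, 219, 159 and 152 all reproduce, and 159 and 152 are averages at the projected rates. The Summary's expected size of 152 for Group 3 does not reproduce, nor does the maximum of 219 in the Group 3 text (3 × 76 = 228). Both equal the Group 4 values.

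**2. Sums.** 159 + 152 = 311. 228 + 219 = 447. 447 / 311 = 1.44. Four-group maxima: 81 + 423 + 228 + 219 = 951. The protocol prints none of these totals.

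**3. How often the third stage is needed.** Exact binomial calculation of the Section 6.3 rule (stop when the score statistic is below −2.289, that is, when the upper score limit is below the null rate):

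| | Group 3 | Group 4 |
|---|---|---|
| Third stage enrolled, no effect | 98.6% | 99.2% |
| Third stage enrolled, projected rate | 39% at 16.25% (40% at 16.3%) | 40% |
| Mean size, no effect | 226.2 | 218.1 |
| Mean size, projected rate | 159.7 (160.5 at 16.3%) | 161.1 |

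If the two groups are treated as independent, the total exceeds 311 when the pair of final sizes is 152 + 219, 228 + 146 or 228 + 219. At 16.3% and 7.5% that has probability 0.126 + 0.162 + 0.160 = about 45%.

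**4. Power if enrolment closed at 159 and 152.** Same exact method, Group 3 at 16.25%:

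| | Group 3 | Group 4 |
|---|---|---|
| Full three-stage design | 85.3% | 86.4% |
| Looks 1 and 2, last look at 159 / 152 | 67.6% | 66.6% |
| Only the two completed looks (152 / 146) | 60.8% | 59.9% |

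**5. Expected size under no effect, by the plan's own approximation.** The ratio is (1 + 0.989 + 0.981) / 3 = 0.990, so 0.990 × 228 = 225.7 and 0.990 × 219 = 216.8.

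**The case against.** The maxima are not hidden. The Section 6.1 table prints 228 and 219 for exactly the two current groups, and the Summary's design paragraph prints the same two numbers with the reason why the expected size is lower. The headline and Section 3.2 do use the word expected. Each group is a separate hypothesis with its own size, so a total is not needed to define the design. All of this stands. It limits the point to where and how the size is stated; the sample-size calculation itself is unaffected.

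Three stronger readings are tempting, and the documents do not support them.

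- **That 311 was the number used for approval, plasma supply or accrual planning.** No section says which number was used for any of these.
- **That the trial is underpowered.** The 67% arises only if enrolment closes at 159 and 152. Nothing directs that: Section 6.1 plans three stages, and Section 6.3 continues enrolment when the limit is not met.
- **That 447 is a fixed commitment.** Section 6.3 allows the sample size to be adjusted at the interim analysis, and Sections 3.3 and 8.7 allow early closure for other reasons. It is the planned maximum.

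Nor do 159 and 152 hold whenever plasma works: a larger effect than projected gives smaller averages, and a smaller effect gives larger ones.

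**Conclusion.** The point holds as an inconsistency in the stated size. The Summary headline and Section 3.2 report averages that apply at 16.3% and 7.5%, without that condition and without the maximum. The Summary's design paragraph and Section 3.1 still describe four groups where two exist. Group 3 has conflicting expected sizes (152 and 159) and conflicting maxima (219 and 228); the recalculation, the stage size and the Section 6.1 table support 159 and 228.

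The planned maximum is 447, 44% above the 311 that a reader would add up from Section 3.2. It is reached almost always if plasma has no effect, and each group needs its third stage in about 40% of trials at the projected benefit. The stated 80% power rests on that third stage being available.

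These figures assume the Section 6.3 rule is applied as written at the planned stage sizes, with no sample-size adjustment, no closure for other reasons and no dropout (Section 5.4 anticipates none). The design behind the numbers is reproducible. The text should be corrected, but no redesign is needed.

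**What to change.** - **Summary headline and Section 3.2:** state up to 228 (Group 3) and up to 219 (Group 4), 447 in total; expected 159 and 152 at the projected rates of 16.3% and 7.5%.
- **Optional addition:** if an expected size under no effect is given, use the same normal approximation as the plan, about 226 and 217. Exact-binomial values (226 and 218) should not stand beside 159 and 152, because the exact method gives about 160 and 161 at the projected rates.
- **Summary, design paragraph:** delete the Group 1 and Group 2 figures (81, 423, 56, 296) and the reference to four groups; change the Group 3 expected size from 152 to 159.
- **Section 3.1:** change the number of treatment groups from 4 to 2.
- **Section 6.1, Group 3 text:** change the maximum from 219 to 228.

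The cost is wording only. The headline enrolment figure becomes less favourable, and no patients are added to the Section 6.1 design.

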8.7 Closure of the Study

This study may be prematurely terminated, if in the opinion of the investigator there is sufficient reasonable cause.

Circumstances that may warrant termination include, but are not limited to:

- Determination of unexpected, significant, or unacceptable risk to patients
- Failure to enter patients at an acceptable rate
- Insufficient adherence to protocol requirements
- Insufficient, incomplete and/or unevaluable data
- Determination of efficacy based on interim analysis

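### The interim rule in Section 6.3 has no futility criterion: by that rule stage 3 is enrolled even when the final efficacy limit is out of reach (at the null rates, 19.8% of Group 3 and 59.2% of Group 4 trials)

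*Combined protocol and SAP*

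**What the plan says.** The Protocol Summary (Overview of Study Design) gives one reason for enrolling fewer than the maximum: "Due to the likelihood that we may terminate a study for efficacy after an interim analysis, the expected numbers of enrollment" are smaller than the maxima.

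Section 6.3 compares the upper score confidence limit, with critical value 2.289, with the null proportion. If the limit is below the null, efficacy is concluded and enrolment in that group ends. Otherwise: "If the upper limit is greater than the null proportion, we will proceed to the second stage of enrollment". For the later looks: "The same evaluation will be replicated in the second interim analysis, as well as in the final analysis should we proceed to this step". No futility limit, conditional power rule or curtailment rule appears in the documents.

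Section 8.7 lists grounds for early closure. The only one tied to an interim result is "Determination of efficacy based on interim analysis". The same section also allows the investigator to end the study for any cause judged sufficient, and says that its list is not exhaustive.

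Section 6.1 gives the design for Group 4: "Among healthcare workers 14.8% of cases were classified as evolving to severe or critical per the Chinese epidemiological review"; the risk "will be reduced by a factor of .5 to 7.5% or lower". There are three stages with 73 patients each, and the section states the resulting sizes: "Our design leads to the maximum size of 219 patients after completing 3-stage of enrollment and the expected size is 152 patients". For Group 3 the null is 25%, the projected rate is 16.3%, and each stage has 76 patients.

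**The concern.** The plan works out what happens if plasma works: the expected sizes of 159 and 152 apply at the projected proportions. It does not say what to do if plasma does not work, although Section 1.5 names that possibility. By the written rule, another 76 or 73 patients would then be enrolled and transfused for a primary test that may already be lost. Group 4 includes health care workers without symptoms. Section 1.5 expects infusion risks to be low, but it lists TACO, TRALI and anaphylaxis among them. The answer would also come later.

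This is not the harm case. In Group 4, 21 of 146 is 14.4%, which is below the 14.8% null, and the score interval at 2.289 runs from 9.0% to 22.3%. A rule acting on the lower limit would not trigger.

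**Working it through.** **Inputs.** Nulls 0.25 and 0.148; projected rates 0.25 × 0.65 = 0.1625 (printed as 16.3%) and 0.075; stages of 76 and 73 (6.1); critical value 2.289 at every look (6.3). For Group 3, I use the table's maximum of 228 = 3 × 76. The Group 3 text in 6.1 prints 219, which does not match its own stage size.

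**1. The plan's own sizes.** A three-look Pocock design with a one-sample Z test, critical value 2.289 and the null variance under both hypotheses needs these sizes for 80% power:
- Group 3, at 16.3%: 76 per stage, maximum 228, power 80.2%, expected size 159.7 (stated 159).
- Group 4: 73 per stage, maximum 219, power 80.5%, expected size 153.1 (stated 152).

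The maxima reproduce and the expected sizes agree to about one patient, so the check uses the sponsor's design.

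**2. Efficacy limits.** The upper score limit is below the null p0 when (x/n − p0) / √(p0(1 − p0)/n) < −2.289. The largest counts that qualify are:

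| | Look 1 | Look 2 | Final |
|---|---|---|---|
| Group 3 | 10/76 | 25/152 | 42/228 |
| Group 4 | 3/73 | 11/146 | 20/219 |

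For example, the upper limit is 0.1459 at 20/219 and 0.1513 at 21/219, against 0.148. Final success is therefore impossible from 43 (Group 3) or 21 (Group 4) progressions onward.

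**3. How often this has happened by look 2.** I used exact binomial convolution over the stages, removing trials that had already stopped for efficacy:
- Group 3, 43 or more of 152: 19.8% at a true rate of 25%; about 4% at 22% and 50% at 28%.
- Group 4, 21 or more of 146: 59.2% at a true rate of 14.8%; 12% at 11%, 34% at 13%, 90% at 18%.

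**4. Expected enrolment at the null.** E(N) = n × [1 + P(stage 2) + P(stage 3)].
- Group 3: 76 × (1 + 0.9912 + 0.9856) = 226.
- Group 4: 73 × (1 + 0.9965 + 0.9915) = 218.

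**5. Adding a stop at look 2, at 38/152 or 20/146.** At those counts, final success needs at most 42 − 38 = 4 progressions in 76 patients, or 20 − 20 = 0 in 73. At the projected rates the chance is 0.34% in each group; for Group 4 it is 0.925^73 = 0.0034. At the null rates, P(stage 3) falls to 0.4546 and 0.3108:
- Group 3: 76 × (1 + 0.9912 + 0.4546) = 186.
- Group 4: 73 × (1 + 0.9965 + 0.3108) = 168.

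Power at the projected rates moves from 0.852888 to 0.852882 and from 0.863634 to 0.863623. At the printed 16.3%, Group 3 power is 0.848 with or without the rule. False-efficacy error stays at 0.0217 and 0.0144.

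**6. Minimum version: stop only when success is impossible (43/152, 21/146).** Power is unchanged, because those trials cannot succeed. Expected enrolment at the null is 211 and 175.

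**The case against.** A reader might infer that the trial can stop early only for efficacy and must otherwise run to its maximum. The documents do not support that. Section 8.7 gives the investigator open-ended discretion to close the study, on a list that is expressly not complete, and it includes unacceptable risk to patients. Continuing is the default of the 6.3 rule, not a duty. Since the proposed rule is non-binding, the decision would stay with the same people. This objection stands as far as it goes. It does not supply a threshold: 8.7 gives no futility criterion, and Section 7.1.2 says that the investigator is also the sponsor. A criterion fixed in advance is worth more than unguided discretion, above all in an uncontrolled comparison with a historical rate.

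A reader might also take 59% as the figure for the trial. It holds for Group 4 only, and only at a true rate of exactly 14.8%. That figure is the share of health care worker cases classed as severe or critical. Whether it is the untreated progression rate of staff who enter with asymptomatic, mild or non-severe disease is an assumption, so the range in step 3 belongs with it.

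Three further points are fair. An efficacy-only Pocock design is a recognised choice. Stage 3 data also serve secondary endpoints, safety and the titer analysis. In Group 3 the argument from a result already fixed supports only a modest saving (226 to 211); the fall to 186 comes from stopping when success is very unlikely, not impossible.

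**Conclusion.** The point holds in this form: the pre-specified interim rule stops only for efficacy and has no futility criterion. By that rule enrolment goes on to stage 3 when the final limit can no longer be met, unless the investigator steps in under 8.7. At the null rates that situation has arisen by the second interim in 19.8% of Group 3 trials and 59.2% of Group 4 trials, and stage 3 is entered in 98.6% and 99.2% of all trials.

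The results rest on the 6.3 rule applied as written, the stage sizes in the 6.1 table, independent patients with a constant progression rate, and an ineffective product meaning a true rate equal to the null. The limits do not depend on the true rate, but the percentages depend on it strongly. This is a cheap improvement that should be made. It is not an error that invalidates the efficacy test.

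**What to change.** Add to 6.3, with a matching line in the 8.7 list, a rule such as: at the second interim analysis, enrolment in the group ends for futility if progressions number 38 or more of 152 (Group 3) or 20 or more of 146 (Group 4); the rule is non-binding, and the counts are recalculated if the null proportion or stage sizes are revised under this section. The last clause is needed because 6.3 allows sample size adjustment at the interim when outside rates change. The efficacy limits stay as they are.

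If the sponsor prefers the least change, stop only at 43 or more of 152 or 21 or more of 146.

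The cost is one sentence in 6.3 and one line in 8.7, with a power loss of about 0.00001 for the main version and none for the minimum version. The real downside is fewer patients for secondary, safety and titer analyses in a group that has in effect failed its primary test. Because the rule is non-binding, enrolment could still continue for those data, but as a stated decision with reasons.
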